#### **7.3.6 Cytokine Release Syndrome (CRS) or CRS-Like Symptoms**

While CRS is a clearly defined syndrome in T cell therapy, it is not known to occur to the full extent in NK cell therapies. However, we have seen immune activation syndromes with other IL-15 products that include fever, and rash. If symptoms occur, CRP, IL-6 and ferritin levels will be assessed. If indicated by the presence of medically significant symptoms and/or high IL-6 levels or any symptoms requiring intervention, steroids are the first line of treatment.

Patients will be monitored for clinical signs and symptoms of CRS through routine daily patient assessments and via the Targeted Toxicities Worksheet ([Appendix VI](#)). Refer to [Section 10](#) for the revised CRS grading system that will be used for this study.

### **7.4 Opportunity for Re-Treatment**

If a patient completes the planned 3 blocks of TriKEs treatment per protocol with lack of disease progression or evidence of a clinical improvement, re-treatment may be an option after discussion with the institutional PI or designee. The patient must continue to fulfill the relevant eligibility criteria in [Section 5](#) and have had no toxicity equivalent to a DLT with the 1st treatment course. Participants would sign a re-treatment consent and be enrolled onto the retreatment protocol CPRC

#2015LS167R, while continuing to be followed for the main study's endpoints as planned.

Eligible patients will receive TriKE at the same or a lower dose level and on the same schedule as initially treated. Treatment must begin within 2 to 4 weeks after completion of the 1st course. Treatment guidelines will be followed per [Section 7](#). Re-treatment patient events will not apply toward dose limiting toxicities (DLTs) or early stopping rule events. Tests and evaluations (with a limited research related sample collection plan) during and after treatment would follow those in [Section 8.1](#) and [Section 8.3](#). This includes frequent assessments for toxicity and survival follow-up through 6 months from the 1st dose of the re-treatment.

Such situations are considered compassionate and would not be included in the statistical analysis.

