#### **7.1.5 Criteria to Continue with GTB-3550 TriKE Block #2 and #3**

A dose limiting toxicity (for any patient, not just dose finding) during the previous block's infusions (defined in [Section 7.2.1](#)) will disqualify a patient from receiving further therapy.

**Disease based treatment decisions:** If after completing Block #1 and Block #2, the patient has clear evidence of disease progression they will be discontinued from study treatment and further treatment with study drug is to be discontinued. Such patients remain fully evaluable for efficacy and toxicity.

To begin a new block, on the day of the planned treatment the patient must:

- not currently meet any disease specific hematologic dose limiting toxicity as defined in [Section 7.2.1](#).
- have an estimated glomerular filtration rate  $\geq 60$  mL/min/1.73 m^2
- have a total bilirubin of  $\leq 1.5$  times the ULN

- have AST and ALT  $\leq$  3 x upper limit of normal, and alkaline phosphatase levels  $\leq$  2.5 x upper limit of normal
- be afebrile (defined as a temperature of  $\leq$  101°F)
- have room air O2 saturation  $\geq$  88%
- have a blood pressure  $\geq$  100/65 mm/Hg
- have no signs or symptoms of infection

If the above criteria is not met, treatment must be delayed for appropriate supportive care and clinical assessment. The study drug may begin the following day, if the above criteria are met and, in the opinion of the clinical provider it is safe to proceed. Otherwise delay 1 week from the planned start and reassess at that time.

Patients unable to begin treatment after a 1 week delay will be permanently discontinued from treatment and followed per [Section 7.6](#).

The start of Block #2 or Block #3 may be delayed for up to 1 week (i.e. start 1 week later than planned) to allow for the resolution of any treatment or non-treatment issues (i.e. URI, UTI, etc.) or for holiday/scheduling issues.

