## 10.2 Event Documentation

Event monitoring and documentation begins with the 1st dose of TriKEs.

For the purposes of this study, selected expected adverse events will be assessed using the Targeted Toxicity Worksheet ([Appendix VI](#)) and any unexpected events will be collected at the following time points in relation to the GTB-3550 TriKE infusions through Day 29:

- Prior to the infusion start of each 24 hour infusion (i.e. Day 1, 2, 3, 4, and Day 8, 9, 10, 11, and Day 15, 16, 17, 18)
- At the end of the final infusion of each block (i.e. Day 5, Day 12, Day 19)
- Day 22
- Day 29

At each time point, the worst grade of the targeted toxicity since the last assessment or the previous 24 hours (whichever is shorter) will be recorded in addition to any unexpected toxicities felt at least possibly related the study treatment.

If a patient discontinues study therapy early or otherwise does not receive treatment as planned, the targeted toxicity assessment time points may be adjusted or eliminated; however, patients must be assessed for a minimum of 28 days from the 1st dose of study drug.

If a patient is not abiding by the standard of care study calendar ([Section 8.1](#)), collection of the corresponding targeted events (and research related samples) also may be altered or discontinued on an individual patient basis, as appropriate.

Monitoring for adverse events will end after the last targeted assessment; however, the investigator is obligated, upon knowledge of, to report any event meeting the criteria in [Section 10.5](#).

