#### **10.4 Early Study Stopping Rules - Event Documentation and Reporting (Phase II Dose Expansion)**

Early study stopping rules for the Phase II dose expansion component patients are:

- Grade 4-5 non-hematologic, non-relapse, non-infectious toxicity (except fever) by 42 days after the start of the first GTB-3550 TriKE treatment block
- Non-relapse, non-infectious treatment related mortality (TRM) within 60 days of starting GTB-3550 TriKE treatment

Meeting either stopping rule criterion temporarily will halt study enrollment until the event is fully evaluated and the Principal Investigator and GT Biopharma make a decision regarding the continuation of the trial. Any patients currently receiving treatment may continue after discussion with the study PI and GT Biopharma.

Events that count toward dose limiting toxicity and early stopping rules do not necessarily constitute a serious adverse event requiring expedited reporting and should be reported as such only if they meet the criteria for expedited reporting as defined in [Section 10.6](#).

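### Section 7.4 leaves re-treated patients' events out of the Phase II stopping rules, while Sections 10.4 and 12.4 count by time from first treatment without exception

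*Combined protocol and SAP*

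**What the plan says.** Section 7.4 lets a patient who completes all three blocks without progression, or with clinical improvement, and without DLT-equivalent toxicity receive a second course. On timing it says "Treatment must begin within 2 to 4 weeks after completion" of the first course. On safety counting it says "Re-treatment patient events will not apply toward dose limiting toxicities (DLTs) or early stopping rule events", with no reference to any time window. On analysis it says "Such situations are considered compassionate and would not be included in the statistical analysis". It also keeps these patients in the main study, "while continuing to be followed for the main study's endpoints as planned".

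Section 10.4 sets two Phase II stopping events. One is Grade 4-5 non-hematologic toxicity up to 42 days from the start of the first block, leaving out relapse and infection. The other is "treatment related mortality (TRM) within 60 days of starting GTB-3550 TriKE treatment", with the same two causes left out. Section 12.4 repeats both definitions and attaches the boundary 2/3, 3/8, 4/13, 5/20, 6/26 or 7 events for 27 patients. It states a stopping probability of at most 10% at a 10% event rate and of 88% at a 30% rate. Neither section mentions re-treatment.

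The primary Phase II endpoint (Sections 1.1 and 12.1) is best response by Day 42, assessed between Day 21 and Day 42.

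**The concern.** The two stopping events are defined by the calendar, but the exclusion in Section 7.4 is defined by the patient's status. Where the two overlap, the same event counts under one section and not under the other. A treatment-related death on Day 50 in a re-treated Phase II patient meets Section 10.4 and is removed by Section 7.4. The exclusion covers events in re-treatment patients without regard to cause, so it can also be read to remove a late toxicity of the first course that appears after re-dosing. Two sites could report the same death differently.

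At stake is the sensitivity of the Phase II safety boundary. Leaving out in-window events can only lower the chance of stopping below the stated 88%, or leave it unchanged.

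A secondary and narrower gap concerns the response endpoint. Section 7.4 continues follow-up for the main endpoints and also excludes re-treatment from the analysis, but gives no date at which response assessment is cut off.

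**Working it through.** **Step 1: when re-treatment can start.** Section 10.2 places the end of the last infusion: "At the end of the final infusion of each block (i.e. Day 5, Day 12, Day 19". The undelayed course therefore ends on Day 19. Section 7.1.5 allows slippage: "The start of Block #2 or Block #3 may be delayed for up to 1 week". Section 7.4 adds 14 to 28 days after completion.

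| Block delays | Course ends | Re-treatment starts | Days left to Day 42 (earliest / latest start) | Days left to Day 60 (earliest / latest start) |
|---|---|---|---|---|
| None | Day 19 | 19+14 to 19+28 = Day 33-47 | 10 / 0 | 28 / 14 |
| One | Day 26 | Day 40-54 | 3 / 0 | 21 / 7 |
| Both blocks | Day 33 | Day 47-61 | 0 / 0 | 14 / 0 |

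Days left are counted inclusively, for example 42 - 33 + 1 = 10 and 60 - 33 + 1 = 28. The earliest start is Day 33, so the 28-day DLT window never overlaps.

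**Step 2: reproduce the plan's figures.** An exact sequential binomial recursion was run over 27 patients. It stops when events reach 2 by patient 3, 3 by patient 8, 4 by patient 13, 5 by patient 20, 6 by patient 26, or 7 by patient 27. It gives 9.7% at a 10% rate and 87.8% at a 30% rate. Both stated figures reproduce, with every event inside the window counted.

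**Step 3: effect of leaving events out.** Let u be the share of in-window events that go uncounted. The countable rate is 0.30 × (1 - u), and the same recursion gives:

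| u | 0 | 5% | 10% | 20% | 30% |
|---|---|---|---|---|---|
| P(stop), true rate 30% | 87.8% | 84.3% | 80.1% | 69.8% | 57.0% |

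**Step 4: plausible values of u.** The documents give neither the share of patients re-treated nor the timing of events. The assumptions here are that events are uniform over the window, that 20%, 40% or 60% of patients are re-treated, and that late events fall in re-treated patients in proportion to their number. Then u = (days left in window / window length) × share re-treated. For example, with the TRM rule, a Day 33 start and 60% re-treated, u = 28/60 × 0.60 = 28%. The countable rate is 0.30 × 0.72 = 21.6%, and P(stop) is 59.7%.

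| Rule | Start | 20% re-treated: u, P(stop) | 40%: u, P(stop) | 60%: u, P(stop) |
|---|---|---|---|---|
| TRM, Day 60 | Day 33 | 9.3%, 80.7% | 18.7%, 71.3% | 28.0%, 59.7% |
| TRM, Day 60 | Day 40 | 7.0%, 82.7% | 14.0%, 76.3% | 21.0%, 68.6% |
| TRM, Day 60 | Day 47 | 4.7%, 84.5% | 9.3%, 80.7% | 14.0%, 76.3% |
| Toxicity, Day 42 | Day 33 | 4.8%, 84.5% | 9.5%, 80.6% | 14.3%, 76.0% |
| Toxicity, Day 42 | Day 40 | 1.4%, 86.8% | 2.9%, 85.9% | 4.3%, 84.8% |
| Toxicity, Day 42 | Day 47 | 0, 87.8% | 0, 87.8% | 0, 87.8% |

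**Step 5: the response endpoint.** Section 4 ties re-treatment to benefit seen at the first disease reassessment, so that assessment comes before re-dosing. Section 8.3 lets the same marrow serve as the re-treatment baseline. The second course's own reassessment (its Day 21-42) falls on main-study Day 33 + 20 = 53 at the earliest and Day 47 + 41 = 88 at the latest for an undelayed first course, always after Day 42. Three things could still reflect the second course:

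- blood counts (MDS hematologic improvement) or serum tryptase (mastocytosis) on Day 33-42;
- an unscheduled marrow on those days;
- confirmation of the 4-week durability that Appendix III requires for MDS responses.

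No section says whether re-treatment is the new therapy that ends response follow-up in Section 8.1 footnote 6, or the new treatment that ends direct participation in Section 7.6.

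**The case against.** The best defence is that Section 7.4 is explicit and specific. Re-treatment is compassionate, has its own consent and protocol number, and lies outside the single planned course that the rules monitor. On that view it is a deliberate exception to Section 10.4, and only a cross-reference is missing. Deaths are still recorded as serious events under Section 10.5 and reach the sponsor within a day or so under Sections 10.6 and 10.7. Meeting a boundary only halts enrollment temporarily.

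Some of this stands. Excluding events caused by a second course is a defensible choice, and nobody would be blind to a Day 50 death. But serious-event reporting does not feed the boundary, and the 88% in Section 12.4 assumes that the whole window is counted. Nor does the exclusion separate second-course events from late first-course events.

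The objection to the size also has force. Re-treatment requires all three blocks, no progression, no DLT-equivalent toxicity and renewed eligibility, so the share re-treated may be small in this population. These patients are also selected for having tolerated the drug. If the monitored rate means first-course mortality, deaths caused by re-dosing were never part of the 30%, and only first-course deaths after re-dosing are lost.

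A reader might infer that the Day 42 response is materially contaminated by second courses. The documents do not support that: the first reassessment precedes re-dosing, the next scheduled one falls after Day 42, and Section 7.4 already excludes re-treatment from the analysis.

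**Conclusion.** The conflict between Section 7.4 and Sections 10.4 and 12.4 is real and should be resolved before Phase II. For an undelayed course, re-treatment always starts inside the 60-day TRM window. It starts inside the 42-day toxicity window only on Day 33-42. With one block delayed the start is Day 40-54, and the overlap with the toxicity window is at most 3 days.

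The direction of the effect is certain, but its size is not. Under the assumptions in the working, the stopping probability at a true 30% rate falls from 87.8% to about 81%-60% (TRM, Day 33 start), 85%-76% (TRM, Day 47 start) or 85%-76% (toxicity, Day 33 start). It does not change for the toxicity rule when re-treatment starts after Day 42.

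Two stronger readings should be avoided. A reader might infer that every re-treatment start falls inside both windows; starts on Day 43-47 miss the toxicity window. A reader might also settle on one figure. With half the patients re-treated and 35% of the window lost, the countable rate is 30% × (1 - 0.5 × 0.35) = 24.75% and the stopping probability 72.6%, but that is one assumed scenario within a range.

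The DLT assessment is unaffected, and the stopping rules cover Phase II only. The response gap is a narrow residual that needs a cut-off date; it is not evidence of bias.

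**What to change.** Reconcile Section 7.4 with Sections 10.4 and 12.4 by stating whether events after re-dosing, but within 42 days (toxicity) or 60 days (TRM) of the first dose, count toward the Phase II rules. Counting all of them preserves the stated 88%. If some are to stay excluded, say how a late first-course event is told apart from a second-course event, and restate the operating characteristics in Section 12.4.

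Add a sentence that the primary response uses only assessments made before the first re-treatment dose. It should also say how the 4-week MDS durability is judged when that period runs into re-treatment.

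The cost is about two sentences and no new data: Section 8.2 already schedules stopping-rule assessment to Day 42 and Day 60, and Section 8.1 records survival at Day 60 for this purpose. If all in-window events count, a few more may count toward a temporary enrollment halt.

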## 7.5 Duration of Study Treatment

Patients will receive one treatment course consisting of three sets (blocks) of four consecutive 24 hour continuous infusions GTB-3550 TriKE unless:

- the patient experiences the equivalent of a dose limiting toxicity (see [Section 7.2.1](#) for definition),
- the patient is unable to start Block #2 or #3 within 1 week of the planned date,
- the patient refuses further treatment,
- **Disease based treatment decisions:** If after completing Block #1 and Block #2, the patient has clear evidence of disease progression they will be discontinued from study treatment and further treatment with study drug is to be discontinued.
- In the opinion of the treating investigator, continuing treatment is not in the best interest of the patient.

For patients discontinuing prior to completing 3 blocks, post-treatment activities at Day 22 and Day 29 are shifted earlier to maintain the timing (i.e. 1 and 2 weeks from the start of the final block).

## 7.6 Duration of Study Participation

Direct study participation ends with the end of treatment visit at Day +60 ( $\pm 1$  week) or earlier, if a new treatment is started. For patients not receiving all 3 blocks, the end of treatment visit occurs approximately 6 weeks ( $\pm 1$  week) from the start of the last block.

Further treatment, independent of the study, will be at the treating physician's discretion.

Follow-up will continue for overall survival continues on all evaluable patients through 6 months from the 1st treatment by record review or other means.

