## 4 Study Design

This is a multisite Phase I/II clinical trial of GTB-3550 (CD16/IL-15/CD33) tri-specific killer cell engager (TriKE) for the treatment of CD33-expressing high risk myelodysplastic syndromes, refractory/relapsed acute myeloid leukemia or advanced systemic mastocytosis. Up to 10 study centers may take part in this trial.

Patients receive a single course of GTB-3550 TriKE given as 3 weekly treatment blocks. Each block consists of four consecutive 24 hour continuous infusions of GTB-3550 TriKE followed by a 72 hour break after Block #1 and #2. All treatment is given as an inpatient.

Toxicities are monitored through Day 28 (as assessed on Day 29) with continued toxicity assessment through Day 60. Disease response is assessed by bone marrow biopsy performed between Day 21 and 42 after the start of the 1st infusion. Follow-up for response and survival continues through 6 months from study treatment start.

The study consists of two components. The dose finding component is a modified version of a Phase I trial and the extended component is a modified Phase II trial.

**Dose Finding Component:** The Phase I component uses a continual reassessment method (CRM) to determine the maximum tolerated dose (MTD) of GTB-3550 TriKE. Up to 7 doses levels will be tested. The goal of the CRM is to identify the dose level which most closely corresponds to the targeted dose limiting toxicity (DLT) rate of 20%.

Patients are enrolled in cohorts of 2 beginning at Dose Level 1. A minimum of 1 week must separate each patient. Both patients within a cohort must reach Day 28 (end of the DLT assessment period) prior to enrollment of a subsequent cohort. The study statistician assigns each new cohort of 2 patients to the most appropriate dose level based on updated toxicity probabilities. As enrollment proceeds, each cohort is assigned to an increased, decreased or equivalent dose level based on prior data in the trial until the study sample reaches 30. At this time, the last dose is declared the MTD and the GTB-3550 TriKE dose for the extended component.

**Extended Component:** The primary goal of the extended component is to study the potential efficacy of GTB-3550 TriKE in this patient population. Efficacy is measured using rates of complete and partial remission. A Simon's MiniMax two-stage design is used in this phase. Monitoring guidelines are in place to stop the study early for excessive toxicity.

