## 8.1 Required Standard of Care

Standard of care procedures should be followed for all enrolled patients, including those who are enrolled for retreatment.

Activity	Screening within 30 days of enrollment (within 14 days if for eligibility)	Day 1, Day 8, and Day 15 (start of treatment block)	Daily during infusions (i.e. Day 2-5, 9 12, 16-19)	Day 22	Day 29	Anytime between Day 21 through Day 42	End of Treatment Visit Day 60 (±7 days)	FU for overall survival (through Month 6)
consent	X							
baseline assessment	X							
medical history	X	X		X	X		X	
concomitant meds 	X	X	X	X	X		X	
physical exam	X	X		X	X		X	
vital signs including pulse oximetry	X	X	per Section 7.1.1	X	X		X	
neurologic assessment		X 		X				
provider assessment			X					
survival status							X 	X
assessment of toxicity		X	X	X	X		X	
Karnofsky PS	X				X		X	
height	X							
weight		X (- 5 days)						
CBC/diff/plt	X	X	X	X	X		X	
basic metabolic panel			X					
comprehensive metabolic panel  , magnesium and phosphorus	X	X		X	X		X	
ALT, AST, total bili, albumin 			2 times					
hepatitis B and C screening	X							
INR 	X							
eGFR	X							
Serum pregnancy test for FOCBP within 7 days of treatment start	X							
Disease assessment	X					X		
BM biopsy 	X					X		
Electrocardiogram	X							
Echocardiogram, cardiac MRI or MUGA	X							
Chest/abdomen CT	X							
assessment of response						X		X 

1 - sample to TTL per [Section 8.2](#) at time of each SOC bone marrow biopsy

2 - Neurological assessment daily including basic motor (gait), coordination (steadiness) and cognitive function (alert and oriented) - any abnormalities should be followed up with a detailed neurologic exam.

3 - Albumin, alkaline phosphatase, ALT, AST, bilirubin (total), calcium, chloride, CO2, creatinine, glucose, potassium, protein (total), sodium, urea nitrogen

4 - perform LFTs and albumin twice more during infusion week (in addition to Day of infusion start CMP) = three times during infusion week

5 - survival status at Day 60 for early study stopping rule for expansion component only

6 - until relapse/progression or start of a new therapy, then survival only

7 - document all concomitant medications, including start and stop dates, relative to administration of GTB-3550 TriKE

8- Measure and report prior to commencement of GTB-3550 therapy for information only and not as criteria for inclusion.

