## 12 Statistical Considerations

### 12.1 Study Design and Endpoints

This is a multisite Phase I/II study of GTB-3550 trispecific killer cell engager (TriKE) for the treatment of high risk MDS and relapsed AML. Once the MTD is identified, the objective will be to confirm safety and obtain preliminary estimates of efficacy as measured by the objective response, the **primary trial endpoint** as assessed between Day 21 and Day 42. For AML clinical response includes complete remission with or without hematologic or platelet recovery (CR, CRi or CRp) or partial response. For MDS clinical response includes complete remission, marrow CR (with incomplete peripheral blood count normalization), partial response or hematologic improvement (HI). For advanced systemic mastocytosis response is considered a decrease in mast cell burden in bone marrow or serum tryptase level by at least 30%.

All patients completing Block #1 will be evaluable for DLTs and toxicities. Patients who discontinue therapy prior to completion of both Block #1 and Block #2 will be replaced. Patients completing Block #1 and Block #2, but come off treatment for disease progression, will still be evaluable for efficacy and will not be replaced. If needed a subgroup of patients receiving all 3 blocks will also be evaluated for response as a secondary population. We expect that the number of patients coming off therapy after only completing block #1 will be minimal.

**Secondary trial endpoints** will include toxicity through Day 29 and overall survival (OS) at 6 months from 1st dose of study drug.

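### Section 7.6 restricts 6-month survival follow-up to evaluable patients, in conflict with Sections 4 and 8.1, and its visit shift leaves early stoppers without a fixed Day 60 contact for the TRM rule

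*Combined protocol and SAP*

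**What the plan says.** **Survival follow-up.** Section 7.6 reads "Follow-up will continue for overall survival continues on all evaluable patients through 6 months from the" first treatment, and allows this to be done by record review. Section 4 reads "Follow-up for response and survival continues through 6 months from study treatment start", and the synopsis says the same; neither mentions evaluability. The Section 8.1 schedule applies to all enrolled patients and has a survival column through Month 6.

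**Evaluability.** Section 12.1 makes patients who complete Block #1 evaluable for DLTs and toxicities. Patients who complete Blocks #1 and #2 and then stop for progression remain evaluable for efficacy. It adds: "Patients who discontinue therapy prior to completion of both Block #1 and Block #2 will be replaced". It does not define evaluability for OS. Section 12.1 counts OS from the first dose; Section 12.2 specifies Kaplan-Meier curves without naming a population.

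**Day 60.** The TRM rule in Section 10.4 is "Non-relapse, non-infectious treatment related mortality (TRM) within 60 days of starting GTB-3550 TriKE treatment". Section 8.1 places survival status at the end-of-treatment visit, with footnote 5: "survival status at Day 60 for early study stopping rule for expansion component only". Section 8.2 also runs the TRM assessment to Day 60. Section 7.6, however, says: "For patients not receiving all 3 blocks, the end of treatment visit occurs approximately 6 weeks", plus or minus one week, from the start of the last block. Direct participation ends at Day 60 "or earlier, if a new treatment is started".

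**The concern.** OS is measured from first dose, so its natural population is everyone dosed. If follow-up is limited to evaluable patients, membership depends on what happens after dosing. A DLT-equivalent toxicity or a Grade 3 or 4 infusion reaction ends treatment, so toxicity is one of the routes into the replaced group. Those patients may well differ in prognosis, and leaving them out could distort the 6-month estimate.

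The TRM rule is meant to detect treatment-related deaths over 60 days. Patients who stop early for toxicity are of particular interest to it, yet their last scheduled visit can fall well before the window closes. A qualifying death missed in that gap makes the rule less sensitive than Section 12.4 states.

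**Working it through.** **1. Who is evaluable under Section 12.1**

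| Dosed patient | Toxicity definition | Efficacy definition | Survival follow-up under 7.6 |
|---|---|---|---|
| Stops during Block #1 | not met | not met | not provided for |
| Completes Block #1, stops before completing Block #2 | met | not met | depends on which definition is meant |
| Completes Blocks #1 and #2 | met | met | yes |

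Under Section 4 and Section 8.1 all three rows are followed to 6 months. Membership of the evaluable set guarantees survival only to about Day 5 (end of Block #1) or Day 12 (end of Block #2). The guaranteed interval is short; the larger issue is selection on tolerating treatment.

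**2. When the shifted visit falls**

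Visit day = start day of last block + 42, with a window of ±7 days.

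- Last block is Block #1 (Day 1): 1 + 42 = Day 43, window 36 to 50. This is 10 to 24 days before Day 60.
- Last block is Block #2, on schedule (Day 8): 8 + 42 = Day 50, window 43 to 57. This is 3 to 17 days before Day 60.
- Last block starts on Day 15 (Block #2 one week late, or an on-schedule Block #3 that is not completed): 15 + 42 = Day 57, window 50 to 64. This can fall on either side of Day 60.

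After an early stop, Section 10.2 guarantees toxicity assessment for only 28 days from first dose.

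**3. The plan's own TRM figure**

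Inputs from Section 12.4: 27 patients; stop at 2 events by patient 3, 3 by 8, 4 by 13, 5 by 20, 6 by 26, or 7 in total. Let P(n,k) be the probability of k events in n patients without having stopped:

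P(n,k) = P(n−1,k)(1−p) + P(n−1,k−1)p,

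with any path that reaches the boundary moved to the stopped total.

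- p = 0.10: 9.7% (plan: at most 10%).
- p = 0.30: 87.8% (plan: 88%).

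The stated operating characteristics reproduce. They presuppose that every qualifying death is counted.

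**4. Illustration of missed deaths (shares assumed)**

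If a share f of qualifying deaths is missed and those patients are counted as event-free, the effective rate is 0.30 × (1 − f).

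| f | Effective rate | Stopping probability |
|---|---|---|
| 0 | 0.300 | 87.8% |
| 5% | 0.285 | 84.3% |
| 10% | 0.270 | 80.1% |
| 20% | 0.240 | 69.8% |
| 30% | 0.210 | 57.0% |

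**5. Illustration for OS (all inputs assumed)**

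Take 30 evaluable patients with 40% survival at 6 months (12 alive) and add m replaced patients with survival q. All-dosed OS = (12 + m × q) / (30 + m).

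- m = 2, q = 20%: 12.4/32 = 38.8%.
- m = 6, q = 0: 12/36 = 33.3%.
- m = 2, q = 50%: 13/32 = 40.6%.
- m = 6, q = 50%: 15/36 = 41.7%.

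Restricting the set overstates OS in the first two cases and understates it in the last two. The direction depends on the prognosis of the replaced patients, which the documents do not give.

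**The case against.** The best defence is that one loosely worded sentence in Section 7.6 should not override the rest of the protocol. The synopsis, Section 4 and Section 8.1 all give unrestricted follow-up, and Section 8 has survival status abstracted from the medical record. Replacement in Section 12.1 concerns the enrolment count and does not say that follow-up stops. In Phase I, failing to complete a block because of related toxicity is itself a DLT, so such patients must be assessed. Footnote 5 and Section 8.2 keep the TRM check at Day 60 whatever happens to the visit. Deaths during treatment and follow-up are SAEs under Section 10.5, reportable within 24 hours of knowledge under Section 10.6. Section 12.1 expects few patients to stop after Block #1 alone.

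Much of this stands, and it rules out three stronger readings that a reader might draw:

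- *That a new therapy ends survival follow-up.* It ends only direct participation. Footnote 6 of Section 8.1 continues survival follow-up after a new therapy.
- *That every early stopper's visit precedes Day 60.* A last block starting on Day 15 puts the visit at Day 57, with a window to Day 64. Full completers, with Day 60 ± 7, can also be seen before Day 60.
- *That replaced patients are excluded from OS or from the TRM count by rule.* Block #1 completers are evaluable for toxicity, and Section 12.4 does not exclude replaced patients. For TRM the gap is in ascertainment.

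The defence does not settle which passage a site should follow. The SAE duty covers the follow-up period, and the length of that period for a non-evaluable patient is exactly what the passages leave in conflict. Once follow-up has ended, Section 10.5 requires a death date only when the site learns of it.

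**Conclusion.** The point holds as a conflict between passages and a gap in ascertainment. Section 7.6 restricts survival follow-up where the synopsis, Section 4 and Section 8.1 do not, and no section defines the OS population. Applied as written, Section 7.6 could yield a 6-month OS estimated from first dose in a set selected by post-dose events. The visit shift also leaves patients whose last block was Block #1, or an on-schedule Block #2, with no fixed contact at Day 60.

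The size cannot be derived from the documents, which give neither the number of early stoppers nor the share of deaths that might be missed. The fall from 88% to 80% or 70% assumes that 10% or 20% of qualifying deaths go uncounted at a true rate of 30%. A reader might infer that OS is certainly overstated or that the TRM rule is miscalculated. Neither follows: the OS bias can run either way, and the boundary reproduces. The text should be corrected because the correction is cheap and the two endpoints affected depend on complete death data.

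**What to change.** - **Section 7.6:** replace the restriction to evaluable patients with all patients who received any GTB-3550 TriKE, followed for survival to 6 months regardless of replacement or new therapy.
- **Sections 12.1 and 12.2:** state that OS is estimated from first dose in all dosed patients.
- **Sections 7.6, 8.1 and 12.4:** require vital status, cause of death and relatedness at Day 60 from first dose for every dosed expansion patient, by record review if the end-of-treatment visit has been moved earlier.

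These changes concern data collection and analysis only. The cost is a short amendment, record review (which Section 7.6 already permits) for a few extra patients, and possibly a slightly lower reported OS.
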